## **FUTURE TAPE-STRIP ANALYSIS:**

Tape strips will be obtained to characterize the differential gene expression profile of affected areas with AKN before and after treatment. Comparative gene-expression profiling of the treated and untreated sides will then be performed to characterize the exact molecular pathogenesis of AKN. These samples will be frozen and stored until additional funding sources are obtained to cover the expenses associated with the processing and analyses of the tape strips.

## **RANDOMIZATION:**

Once a subject meets all the inclusion and exclusion criteria, they will be assigned a randomization number on day 0/baseline. Enrolled subjects will be randomized in a 2:1 ratio of Duobrii to placebo.

The randomization will be performed by designated research staff/personnel at the Icahn School of Medicine using a randomization generator. The subjects and assessors (sub-investigators) will remain blinded to individual treatment assignment during the study. Research staff will also be responsible for blinding of the medication.

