## **STUDY DESIGN OVERVIEW:**

Following IRB approval, we will conduct a single center, prospective, double-blinded placebo vs. active-control trial assessing the efficacy of the vehicle vs. Duobrii, respectively, in the management of AKN over 3 months.

Blinding will be performed by pharmacy and research staff. In addition, different investigators will do the clinical enrollment and follow up vs. statistical analysis.

Patients with class I and class II AKN (Appendix C) from our various clinics at our Skin of Color Center will be screened with plan to enroll 30 participants after obtaining written informed consent. In addition, flyer announcement of our trial will be distributed and active patient recruitment will be conducted at various local barber shops and social media platforms (instagram, twitter and facebook) to increase patient recruitment.

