Enrolled participants will be instructed to apply placebo (n=10) vs. active (n=20) to affected area of the occipital scalp for 4 weeks once a day (label use). Each application will be approximately 1g. Following the 4 weeks, participants will be instructed to increase application to twice daily (BID; off-label; at least 8 hours apart) for one week. Investigators will conduct a phone visit on week 5 to discuss any potential side effects with this increased dose. If tolerated, this BID regimen will be carried throughout the length of the study. If BID is not tolerated (if irritation occurs), then Bryhali will be used as a “rescue treatment” once daily for 1 week before the subject returns to BID treatment with Duobrii. If irritation recurs, subjects will be instructed to alternate Duobrii and Bryhali (ie Duobrii BID one day, followed by Bryhali QD the next day, Duobrii BID the next, and so on). Alternating topical steroid use and stepping down topical steroid strength have been known to reduce lesion count in AKN. If irritation continues to persist, then participants will be instructed to use Bryhali QD for five days a week and Duobrii BID two days a week. If participants still experience irritation with this regimen, then subjects will be transitioned entirely to Bryhali QD for the remainder of the study. In case of clearance earlier than the end of the study, participants will be instructed to continue their respective regimen to completion of the study. Gentle hair care regimen will be recommended for duration of the length of the study; with unscented shampoo & conditioner (such as Head & shoulder) and Vaseline to scalp as moisturizer to minimize risk of contact dermatitis. In addition, patients will be instructed to postpone any form of hair coloring or chemical hair processing until after the study is over.

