### **Inclusion criteria:**

1. Male or female subject at least 18 years of age
2. Subject is able to provide written informed consent and comply with the requirements of this study protocol
3. Subjects have AKN class I or II (less than 6.5 cm in width)
4. Subjects who are women of childbearing potential (WOCBP) must have a negative urine pregnancy test at screening and must be practicing an adequate and medically acceptable method of birth control for at least 30 days prior to Day 0 and at least 6 months after the last dose of study. Acceptable methods of birth control include intrauterine device (IUD) oral, transdermal, implanted or injected hormonal contraceptives (must have been initiated at least 1 month before entering the study); tubal ligation; abstinence; barrier methods with spermicide. If not of child-bearing potential, subjects must have a sterile or vasectomized partner; have had a hysterectomy, a bilateral oophorectomy or be clinically diagnosed infertile; or be in a menopausal state for at least a year.
5. Subject is judged to be in good general health as determined by the principal investigator.

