## **INVESTIGATIONAL DRUG SUPPLY:**

Study medication will be given to subjects at their baseline visit and subsequent visits as needed. All study medication will be stored in a secured area at 20° to 25°C.

Unblinded research personnel will dispense study drug in an opaque bag to the subject. Individuals will be instructed not to reveal the study drug to anyone except the unblinded research staff.

Investigators will instruct subjects on how to approximately measure 1g per application.

Amount of product requested:

Duobrii = (2 x 100 g tube) or 200g/subject x 20 subjects

Bryhali = (2 x 100 g tube) or 200 g/subject x 20 subjects

Vehicle= (3 x 60 g tube) or 180 g/subject x 10 subjects

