## **Primary Endpoint**

The primary analysis for the primary endpoint will test for a reduction in lesion counts after 12 weeks of treatment. We will apply the two-sided Wilcoxon test to assess the significance of the difference between pre- and post-treatment median numbers of lesion counts. The secondary analysis will compare the reduction in lesion counts between active and placebo groups after 12 weeks. For this purpose, we will apply the Z-test to verify the hypothesis that the proportions of patients with reduced AKN lesions differ between active and placebo groups. A more comprehensive analysis will adjust a generalized linear mixed-effects model, based on Poisson distribution, including time and treatment group as fixed factors and a random intercept for each subject. This model will include the whole time-course and contrasts of interests will be estimated.

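### AKN class is used neither in the 2:1 randomisation nor in the between-arm lesion analyses, so chance class imbalance with 10 vehicle subjects goes uncorrected

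*Combined protocol and SAP*

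**What the plan says.** The inclusion criteria admit two severity classes: "Subjects have AKN class I or II (less than 6.5 cm in width"). Eligibility is settled before a randomisation number is assigned, so class is available at allocation.

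On allocation, the Randomization section gives the ratio, "Enrolled subjects will be randomized in a 2:1 ratio of Duobrii to placebo", and the mechanism, "The randomization will be performed by designated research staff/personnel at the Icahn School of Medicine using a randomization generator". It mentions no block size, fixed-total list, minimisation or stratification factor.

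The total and the arm sizes are given as fixed numbers. The Study Design Overview has a "plan to enroll 30 participants after obtaining written informed consent" and states "Enrolled participants will be instructed to apply placebo (n=10) vs. active (n=20"). Investigational Drug Supply requests "Duobrii = (2 x 100 g tube) or 200g/subject x 20 subjects" and "Vehicle= (3 x 60 g tube) or 180 g/subject x 10 subjects". Sample Size Considerations bases the between-arm power on the same 20 and 10.

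Under Data Analysis, Primary Endpoint, the primary test is a pre/post Wilcoxon. The between-arm test is described thus: "we will apply the Z-test to verify the hypothesis that the proportions of patients with reduced AKN lesions differ between active and placebo groups". The Poisson mixed model for lesion counts has time and treatment group as fixed factors and a random subject intercept. AKN class appears in neither analysis.

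**The concern.** The hypothesis is improvement relative to placebo, yet the primary test is pre/post. The Z-test and the Poisson model are therefore the only lesion-count analyses that use the randomisation. They rest on 10 vehicle subjects, or about 7 after the assumed 30% dropout. If class is related to response, a different class mix in so small an arm shifts the estimated treatment difference, and no planned analysis corrects for it. The information needed to prevent this is collected at screening and not used.

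A second, smaller matter is that the design, supply and power figures all use 20:10, while the allocation text does not say how that split is to be reached.

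**Working it through.** **1. The plan's between-arm power.** Inputs from Sample Size Considerations: 20 vs 10, 30% dropout, 50-point difference, one-sided 5%. Completers: 20 × 0.7 = 14 and 10 × 0.7 = 7. The control rate is not given; take 25% vs 75% (assumption), so p(1−p) = 0.1875 in each arm.

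- SE = √(0.1875/7 + 0.1875/14) = 0.200.
- Power = Φ(0.50/0.200 − 1.645) = 0.802.

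The stated 80% is reproduced. The worst control rate, one third, gives 0.789.

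**2. Class imbalance with exactly 20:10.** Let K of the 30 subjects be class II, and let x of them fall in the vehicle arm. Then x is hypergeometric (30, K, 10), and the difference in class II share is x/10 − (K − x)/20. K is not in the documents; the assumed range is 6 to 24.

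For K = 15 the difference is (3x − 15)/20:

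- It is zero only at x = 5, with probability 0.300. Any other x gives at least 15 points, so P(at least 10 points) = 0.700.
- At least 30 points requires x ≤ 3 or x ≥ 7. P = 2 × (0.0975 + 0.0225 + 0.0025 + 0.0001) = 0.245.

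| Difference in class II share | K = 15 | Range, K = 6 to 24 |
|---|---|---|
| at least 10 points | 70% | 63% to 71% |
| at least 20 points | 25% | 14% to 44% |
| at least 30 points | 25% | 6% to 25% |

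These figures hold for any 20:10 list that ignores class, blocked or not.

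**3. What an imbalance does to the estimate.** Shift = imbalance × class gap in response. With 30 points and an assumed gap of 20 to 40 points, the shift is 0.30 × 0.20 = 6 points to 0.30 × 0.40 = 12 points. The SE from step 1 is 20 points.

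**4. Precision gained by balancing class.** With half the subjects in each class and a gap g, the variance within class is p(1−p) − (g/2)². The variance ratio, balanced to random, is:

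- g = 0.20: (0.1875 − 0.01)/0.1875 = 0.947, about 5% lower.
- g = 0.40: (0.1875 − 0.04)/0.1875 = 0.787, about 21% lower.

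**5. Arm sizes, only if allocation were unrestricted.** The vehicle count would be Binomial(30, 1/3):

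- P(exactly 10) = 0.153
- P(11 or more) = 0.415
- P(7 or fewer) = 0.167

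Averaging the step 1 power over these splits gives 0.785, against 0.802 at 20:10. A 23:7 split gives 0.723.

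**6. After stratified permuted blocks (K = 6 to 24).** Two block sizes as illustrations:

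| | Vehicle arm | P(exactly 10) | Largest class difference |
|---|---|---|---|
| Blocks of 3 | 9 to 11 | at least 56% | 10 points |
| Blocks of 6 | 8 to 12 | at least 44% | 20 points |

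**The case against.** **The plan does not say that allocation is unrestricted.** This stands. A reader might infer a coin-flip generator that would rarely deliver 20:10. The documents do not support that: the text is silent, and the fixed 10 and 20 in the design fit a blocked or fixed-total list. Step 5 is conditional on that reading, and even then the average cost is about 2 points of power. The supply consequence is also weak. The basic regimen at about 1 g per application uses 28 × 1 + 56 × 2 = 140 g per subject, against 180 g requested. The 1,800 g of vehicle covers 12 full courses by weight, so an 11th vehicle subject need not exhaust it.

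**Large imbalance is not likely.** This stands too. A difference of 10 points is likely; one of 30 points occurs in at most a quarter of trials. Chance imbalance is already reflected in the test's error rate, and either arm may be favoured. A reader might infer that the trial is biased, but it is not, in expectation.

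**No document shows that class predicts response.** Correct, so the size of the gain rests on an assumption.

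**Change from own baseline and the random intercept already deal with severity.** This stands only in part. The responder definition removes the baseline level but not a class difference in the chance of responding. The lesion-count model names time and treatment group without their interaction, so its treatment effect is a between-subject contrast. A random intercept describes variation between subjects; it does not remove a systematic class difference between arms.

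**Conclusion.** The point holds as a modest, worthwhile improvement. Class is known before allocation and is used neither in randomisation nor in the between-arm lesion analyses. With an exact 20:10 split, a class difference of at least 10 points is more likely than not (63% to 71%), and one of at least 30 points is possible (6% to 25%), for 6 to 24 class II subjects of 30. The harm is lost precision and a less clear randomised comparison. The pre/post primary test does not use the between-arm class mix and is unaffected.

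The gain is about 5% to 21% lower variance, assuming equal classes, average response of 75% vs 25% and a 20- to 40-point class gap. It would be negligible if class did not predict response.

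On arm sizes, the supportable statement is that the text does not guarantee 20:10, not that it will be missed.

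**What to change.** **Randomization section.** State that subjects are randomised 2:1 from permuted-block lists, one for each AKN class. Block sizes should be held by unblinded staff and not written in the protocol. This keeps the split near the 20:10 used in the design, supply and power sections. If a restricted list already exists, describe its type without its block sizes and say whether class is used.

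**Data Analysis, Primary Endpoint.** Add class as a fixed effect in the lesion-count model, and stratify the between-arm responder comparison by class, for example with a Mantel-Haenszel test. If allocation is stratified and the test is not, the precision gained does not reach the p-value. A class main effect adjusts for level only; it does not correct for a treatment effect that differs by class.

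**Cost.** There are two lists instead of one, and a line in each of two sections. Small blocks make allocation slightly more predictable, which matters at a single centre where irritation might hint at the treatment. Strata in the responder test are small: about 7 vehicle completers leaves 3 or 4 per class at an even mix. The split can still miss 20:10 by one or two vehicle subjects with blocks of 3 or 6.

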## **INVESTIGATIONAL DRUG SUPPLY:**

Study medication will be given to subjects at their baseline visit and subsequent visits as needed. All study medication will be stored in a secured area at 20° to 25°C.

Unblinded research personnel will dispense study drug in an opaque bag to the subject. Individuals will be instructed not to reveal the study drug to anyone except the unblinded research staff.

Investigators will instruct subjects on how to approximately measure 1g per application.

Amount of product requested:

Duobrii = (2 x 100 g tube) or 200g/subject x 20 subjects

Bryhali = (2 x 100 g tube) or 200 g/subject x 20 subjects

Vehicle= (3 x 60 g tube) or 180 g/subject x 10 subjects

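### The irritation pathway covers all participants but names Duobrii as the product they resume, with no branch for vehicle subjects, so it can move controls onto active drug or make rescue depend on the arm

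*Combined protocol and SAP*

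**What the plan says.** All references are to the combined protocol and SAP.

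- **Blinding.** Study Design Overview describes a "double-blinded placebo vs. active-control trial". Randomization adds: "The subjects and assessors (sub-investigators) will remain blinded to individual treatment assignment during the study".
- **Arms.** Study Design Overview: "Enrolled participants will be instructed to apply placebo (n=10) vs. active (n=20) to affected area of the occipital scalp".
- **Irritation pathway.** The same section sets out the steps for participants and subjects without separating the arms. After one week of Bryhali comes the wording "before the subject returns to BID treatment with Duobrii". Later steps alternate Duobrii and Bryhali by name, then use mostly Bryhali, then Bryhali alone. No step is written for a subject assigned to vehicle.
- **Supply.** Investigational Drug Supply requests "Duobrii = (2 x 100 g tube) or 200g/subject x 20 subjects", "Bryhali = (2 x 100 g tube) or 200 g/subject x 20 subjects" and "Vehicle= (3 x 60 g tube) or 180 g/subject x 10 subjects". It also has unblinded personnel dispense study drug in an opaque bag and tells subjects to disclose the drug only to those staff.
- **Analysis.** Sample Size Considerations, Primary Endpoint and Secondary Endpoints do not mention rescue or data collected after it.

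**The concern.** A vehicle subject who reports irritation on twice-daily use falls under the pathway as worded, but the pathway does not fit that subject, who was never on Duobrii and so cannot return to it. Staff would have to improvise, and each way of doing so affects either the blind or the control arm.

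The hypothesis is a comparison with placebo, and the placebo arm has only 10 subjects. Rescue also bears on the endpoint. To support its alternating step, Study Design Overview says that alternating topical steroids and stepping down their strength lower lesion counts in AKN. A control who receives Bryhali is therefore, on the protocol's own reasoning, receiving something that may change the primary measure. If the arm becomes known instead, DLQI and NRS scores are open to expectation, and lesion counts are too if the counter learns of the rescue.

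**Working it through.** **1. Three readings set side by side**

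| Reading of the pathway | What an irritated vehicle subject gets | What it conflicts with |
|---|---|---|
| Literal: everyone, product names as written | Bryhali, then Duobrii | Assigned treatment; Duobrii is requested for 20 subjects |
| Duobrii arm only | No Bryhali | The unrestricted wording; rescue depends on the arm and can reveal it |
| Everyone, Duobrii meaning the assigned product | Bryhali, then vehicle again | The product named in the text; Bryhali is requested for 20 of 30 subjects; controls receive an active steroid |

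No reading fits all the text. The opaque bag and the unblinded dispenser can shield assessors. They do not shield the subject, who knows whether a second product was given. No masked rescue is described and no matching rescue vehicle is listed.

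**2. Supply figures**

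- Bryhali requested: 2 × 100 g = 200 g per subject, and 200 × 20 = 4,000 g. The plan's figure reproduces.
- The count of 20 equals the Duobrii arm; 30 − 20 = 10 subjects have no stated allotment.
- Possible use: Study Design Overview says "Each application will be approximately 1g". I assume this also holds for Bryhali. Once daily from week 5 to week 12 is 7 × 7 = 49 g. As an upper bound, once daily from week 4 is 8 × 7 = 56 g.
- All 30 subjects at that bound: 30 × 56 = 1,680 g, well under 4,000 g.

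The mismatch is therefore in the stated number of subjects (20 against 30), not in the grams.

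**3. Weight of one control**

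- As randomised: 1/10 = 10% of the arm.
- After the 30% dropout assumed in Sample Size Considerations: 10 × 0.7 = 7 completers, and 1/7 = 14%.

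**4. Illustration only: effect on the between-arm test**

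The documents give no irritation rate and no base response rate. I assume that 25% of controls and 75% of active subjects improve (the 50-point difference in the sample-size text), and that a share c of controls moves to active drug and responds at 75%. The control rate is then 0.25 + 0.5c. Power is one-sided at 5%, by normal approximation:

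Φ{ [(p₁ − p₂) − 1.645 × √(p̄(1 − p̄)(1/n₁ + 1/n₂))] / √(p₁(1 − p₁)/n₁ + p₂(1 − p₂)/n₂) }

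| c | Control rate | Power, 14 v 7 | Power, 20 v 10 |
|---|---|---|---|
| 0% | 0.25 | 73% | 87% |
| 10% | 0.30 | 64% | 79% |
| 20% | 0.35 | 56% | 69% |
| 30% | 0.40 | 47% | 59% |

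The direction is clear, but the sizes rest on my assumptions. Subjects on Bryhali alone might respond less than this.

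**The case against.** The best defence is that Duobrii in the pathway is loose shorthand for the assigned product. Returning to a product implies having been on it, the same section speaks elsewhere of each participant's respective regimen, and Duobrii is requested for only 20 subjects, which argues against a planned switch of controls. On this reading rescue does not depend on the arm and no control is given Duobrii. This is plausible, and it means the passages are not strictly irreconcilable. It does not remove the problem: controls would still receive Bryhali, and the analysis sections do not deal with that.

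Three stronger conclusions are tempting, and the documents do not support them.

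- *Bryhali is restricted to the Duobrii arm.* This is an inference from a matching count. The list is a supply request; it names no arm for Bryhali and sets no dispensing rule.
- *Bryhali is 10 × 200 g short.* The requested total more than covers 30 subjects at the protocol's own amount per application.
- *A rescued subject's probability of being on active drug rises from 2/3 to 1.* That requires the subject to know that only active subjects get Bryhali, and nothing in the text says subjects are told this. The 2/3 is also the probability at randomisation, not the probability given irritation.

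It is also fair to say that the assessors need not be unblinded, since an investigator could refer irritation to the unblinded staff. The protocol does not say that this happens. The week 5 call is assigned to investigators, and the blinded assessors are described as sub-investigators.

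Finally, the planned primary test is a pre/post comparison, with the arm comparison labelled secondary. That limits the damage from controls receiving active drug. Biased lesion counting could still affect the pre/post test.

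**Conclusion.** The point holds as an inconsistency within the protocol. The pathway does not say what a vehicle subject with irritation receives or resumes. Followed literally, it moves controls to active drug; limited to the Duobrii arm, it makes rescue depend on the arm; read loosely, it gives controls an active steroid. One affected control is 10% to 14% of the arm. The overall effect cannot be sized because no irritation rate is given. It falls mainly on the between-arm comparisons and patient-reported outcomes, and less on the pre/post test. The conclusion does not depend on which reading the sponsor intended, nor on the power illustration.

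**What to change.** Reconcile Study Design Overview, Randomization and Investigational Drug Supply on whom the pathway covers and which product subjects resume. The clinical rule is the sponsor's to choose. Then:

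- use an arm-neutral term, such as assigned study product, throughout the pathway;
- align the number of subjects on the Bryhali line with the population covered;
- route rescue dispensing through the unblinded staff already named under Investigational Drug Supply;
- keep lesion counters unaware of rescue use, including what is recorded in the dosing diary and at the week 5 call;
- if controls may receive Bryhali, state under Data Analysis how observations after rescue enter the between-arm comparisons. Arm-neutral wording protects the blind but does not remove the steroid exposure.

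The cost is amendment wording and a revised supply line, with no added subjects. A masked rescue, should the sponsor choose one, would need matching product and cost more; this point does not require it.

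### The requested packs differ by arm and no masking of the tubes is described, which puts the subject-level blind at risk

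*Combined protocol and SAP*

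**What the plan says.** The Study Design Overview calls the trial double-blinded and says "Blinding will be performed by pharmacy and research staff". The Randomization section promises that "The subjects and assessors (sub-investigators) will remain blinded to individual treatment assignment during the study", and adds: "Research staff will also be responsible for blinding of the medication". Neither section says how the medication is to be masked.

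The Investigational Drug Supply section lists the amounts requested. The entry for the active arm is "Duobrii = (2 x 100 g tube) or 200g/subject x 20 subjects". The entry for the placebo arm has a different tube size and count: "Vehicle= (3 x 60 g tube) or 180 g/subject x 10 subjects". The rescue product, Bryhali, is put down as two 100 g tubes for each of 20 subjects.

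The one concealment step in the same section is: "Unblinded research personnel will dispense study drug in an opaque bag to the subject". It is followed by an instruction to subjects: "Individuals will be instructed not to reveal the study drug to anyone except the unblinded research staff". Product is supplied at baseline and at later visits when required. Nothing in the protocol mentions identical containers, repackaging, over-labelling or removal of product names.

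**The concern.** A bag hides the product from anyone watching the hand-over. It does nothing once the subject opens it at home and applies the product daily for 12 weeks. If the tubes are used as requested, the two arms hold visibly different packs, and a subject who sees a product name, or learns which pack goes with which arm, is unblinded.

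The outcomes most exposed are those the subject reports: DLQI, the pain and itch NRS, and the symptom survey. The Secondary Endpoints analysis compares these between groups. A subject who suspects the arm may also adhere or drop out differently, or let the arm slip to an assessor, and by that route the between-arm lesion comparison could be touched. Such a loss cannot be repaired in the analysis, so it has to be settled before product is dispensed.

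**Working it through.** **Inputs.** Tube sizes and counts are from Investigational Drug Supply. From the Study Design Overview: about 1 g per application, once daily for 4 weeks (28 days), then twice daily to week 12 if tolerated (56 days). The 50% compliance floor is from the section on discontinuation and withdrawal.

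**The plan's own totals reproduce.**

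- Duobrii: 2 × 100 = 200 g per subject; × 20 = 4,000 g.
- Vehicle: 3 × 60 = 180 g per subject; × 10 = 1,800 g.
- Bryhali: 2 × 100 = 200 g per subject; × 20 = 4,000 g.

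**Planned use per subject, either arm, with full tolerance and completion.** 28 × 1 g + 56 × 2 g = 28 + 112 = 140 g.

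**When tubes run out.** After day 28 the amount used by day d is 28 + 2(d − 28). Setting this equal to the tube content gives:

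| | Duobrii (100 g tubes) | Vehicle (60 g tubes) |
|---|---|---|
| Tubes opened for 140 g | 2 | 3 |
| First tube empty | 28 + 72/2 = day 64 | 28 + 32/2 = day 44 |
| Second tube empty | not reached | 120 g: 28 + 92/2 = day 74 |
| Left over at day 84 | 200 − 140 = 60 g | 180 − 140 = 40 g |

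The week 8 visit is day 56. By then 28 + 2 × 28 = 84 g has been used. A vehicle subject is already on a second tube, while a Duobrii subject still has 100 − 84 = 16 g in the first. So if all product is issued at baseline, the number of tubes differs on day 0. If it is issued when needed, the time of resupply differs.

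**Lower use.** At the 50% compliance floor, spread evenly, total use is 70 g. A Duobrii subject opens one tube and a vehicle subject two, the second at about day 74 (14 + (74 − 28) = 60 g). The times shift but the arms still differ.

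**Rescue product.** Bryhali is requested for 20 subjects, the number assigned to Duobrii, with none for the 10 on vehicle. The irritation steps in the Study Design Overview refer only to Duobrii and Bryhali and do not say what applies to a vehicle subject. Receipt of rescue product could therefore point to the arm as well.

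**The case against.** The tempting stronger reading is that subjects can tell their arm, so the trial is not double-blind. The documents do not support that, for three reasons.

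- The figures are amounts requested, not a description of what reaches the subject. Two sections give blinding to pharmacy or research staff, so undocumented repackaging or over-labelling cannot be excluded.
- In a parallel-group trial each subject normally sees only their own pack. Size and number reveal the arm only to someone who knows which pack belongs to which arm, and the text does not say whether the tubes carry a product name. Subjects who have used Duobrii on the scalp are excluded, which lowers the chance of recognition.
- A reader might take the instruction not to reveal the study drug as an admission that subjects know what they have. The protocol uses that term for whatever is dispensed, so the sentence can simply mean keeping the product from assessors. Rewording it would add little.

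The reach is also limited. The primary endpoint is a lesion count, the assessors are to be blinded, and the primary analysis is a pre/post comparison rather than a contrast between arms. The 140 g figure assumes that every subject tolerates twice-daily use and completes, although the plan has step-down branches and allows 30% dropout.

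All of this stands and makes the conclusion conditional. It does not remove the point: the supply plan, as written, works against the blind, and the text contains no step that offsets it.

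**Conclusion.** The point holds in conditional form and should be acted on. Unless the tubes are masked by a method the documents do not describe, the packs differ by arm in size (100 g against 60 g), number (two against three) and replacement time (first tube empty at about day 64 against day 44 under full planned use). That puts at risk the subject-level blind promised in the Randomization section and the between-arm comparisons of DLQI, NRS and symptoms. The pre/post lesion analysis is much less exposed.

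The days rest on about 1 g per application, full tolerance of twice-daily use, full compliance and one tube used at a time. The differences in size and number requested rest on none of these. No bias has been quantified, and the documents give no basis for doing so.

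**What to change.** In the Randomization and Investigational Drug Supply sections, require that both arms be dispensed in containers that look alike, with the same size, number and fill, and that carry only the subject number. This can be done by requesting vehicle in a tube that matches Duobrii or by having the pharmacy repackage both. If neither is possible, over-label both products to hide their identity and state plainly that container size still differs. If masking is already planned, a sentence describing it is enough.

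Separately, reconcile the rescue steps in the Study Design Overview with the Bryhali request for 20 subjects, and state how rescue supply is kept from revealing the arm. Matching the Duobrii and vehicle tubes alone would leave that route open.

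The cost is a changed vehicle request or some pharmacy work. Equal planned use in the two arms does not show that matching tubes can be obtained. The documents are silent on availability, so the sponsor needs to confirm it.
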